We have successfully used the TOF cuff in the BLISS 2 and Neuropa studies.(7, 8) We find it to be far superior in ease of use over AMG. However, several reviewers questioned the validity of the device during the review process of both studies. A small validation study the TOF cuff has been conducted several years ago and produced acceptable bias and limits of agreement when compared to mechanomyography during recovery of a moderate neuromuscular block. However, the TOF cuff was

not assessed during deep neuromuscular block and not compared to EMG and the authors concluded that additional validation of the device is necessary.(6)

In this study we intend to further validate the TOF cuff and compare it to EMG during recovery of both moderate and deep neuromuscular block. We will study patients of normal and high body mass index values.

2. Objectives

To compare the bias, limits of agreement and precision of the TOF cuff relative to EMG during recovery of moderate and deep neuromuscular block in patients with normal body mass index and morbidly obese patients.

Hypothesis

The TOF cuff behaves similarly to EMG in terms of bias, limits of agreement and precision when comparing the TOF cuff to EMG.

3. Study design

This is an observational, non-inferiority trial in which we will compare the TOF cuff device to electromyography (EMG). We will do this in 100 patients with $BMI < 30 \text{ kg/m}^2$ and 50 patients with $BMI > 35 \text{ kg/m}^2$. The protocol was amended (19-11-2018) to include 50 extra patients to investigate relative bias between ipsi- and contralateral comparisons between TOF Cuff and EMG in patients with normal BMI. Total number of included patients will be 250. The preliminary analysis after 100 patients showed that a significant difference occurs in the comparison between the TOF Cuff and the EMG regarding the time to full recovery of neuromuscular block. The time to complete recovery is clinically the most relevant outcome. To increase emphasis on time until full recovery, the protocol was amended (19-6-19) to include 50 patients in the LUMC which were originally scheduled for the NOK. In the NOK sugammadex is routinely administrated which disables evaluation of the time until complete recovery.

All patients will receive general total intravenous anesthesia (propofol/remifentanil/rocuronium). Patients will have the TOF cuff and EMG placed on one extremity (hand for EMG, upper arm for TOF cuff).

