6. STUDY MEASUREMENTS

General

- Patient characteristics including age, gender, weight, height, BMI, ASA class, underlying disease, medication, comorbidity.
- Duration of surgery and anesthesia;
- Drug dosages and administration times (propofol, opioid, muscle relaxant, reversal agent, other agents used during anesthesia);
- Temperature (central and periferal)
- Time of extubation

Neuromuscular data

Group 1

- Onset:
 - T1 90% depression time will be recorded after administration of rocuronium for all devices
- Recovery:
 - Time to reappearance of T1, T2, T3 and T4
 - Time to T1=25%
 - Time to TOF ratio 0.9
 - Continuous comparisons between the devices at 30 seconds intervals (as outlined before) until TOF ratio 1.0

Group 2

- Onset:
 - T1 90% depression time will be recorded after administration of rocuronium for all devices
- Recovery:
 - Continuous comparisons between the devices at 5 minutes intervals (as outlined before) between PTC 1-10
 - Continuous comparisons between the devices at 30 seconds intervals (as outlined before) until TOF ratio 1.0 after reversal.

7. Statistics

Recovery of neuromuscular block will be compared by the Bland–Altman analysis for repeated measurements for TOF cuff vs. EMG (See Olofson et al.(10)). This analysis allows estimation of agreement between the devices by estimating bias (D) and the 95% limits of agreement (L). Small bias and narrow limits of agreement indicate strong agreement. Additionally, this analysis accounts for the effect of instrumental imprecision by evaluating the repeatability coefficient of each device. A small repeatability coefficient indicates high precision of the device. The limits of agreement capture 95% of differences between the compared devices. We defined clinically acceptable agreement as a bias <0.025 and limits of agreement within -0.050 to 0.050 .

The protocol was amended (19-11-2018) to include 50 extra patients to investigate relative bias between ipsi- and contralateral comparisons between TOF Cuff and EMG in patients with normal BMI. Bias of ipsi- and contralateral comparisons of TOF Cuff vs. EMG will be compared. A relative bias of <5% is defined acceptable.

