7.1 Sample size

Previous results of Rodiera et al. yielded a bias (D) of -0.02 and limits of agreement (L) of -0.035 to -0.012 for the comparison of TOF cuff vs EMG at a TOF ratio of 0.7 and D 0.05 and L 0.04 – 0.06 at TOF 0.1.(6) We are not informed about D and L during deeper levels of neuromuscular block, and at TOF ratio 0.9 which is a clinically important level for safe extubation of a patient. Furthermore, precision was not assessed in this study and no comparisons were made with AMG and EMG.

We will therefore perform a pilot study with 200 patients (100 patients with normal BMI ($< 30 \text{ kg/m}^2$) and 100 patients with morbid obesity ($>30 \text{ kg/m}^2$)) to ensure that reliable estimates of repeatability coefficient (r), bias (D), and limits of agreement (L) are obtained. After 100 patients (50 non-obese/50 obese) we will perform an interim analysis and calculate the remaining number of patients needed to complete the study.

The protocol was amended (19-11-2018) to include 50 extra patients to investigate relative bias between ipsi- and contralateral comparisons between TOF Cuff and EMG in patients with normal BMI. The total number of included patients will be 250. A sub analysis of the first 20 patients shows that it takes 30 (SD 18.0) minutes until spontaneous recovery to a Tof Ratio of 0.9 is achieved. The EMG group required 47 minutes. To exclude possible outliers in our previous study we expect a mean time to a Ratio 0.9 of 42 minutes. With an α of 0.05 and β of 0.9 we require 24 patients. In the same sub analysis we saw that approximately half of the patients require additional muscle relaxants,

meaning that complete recovery is not achieved in half of the cases. In order to acquire a proper sample size to compare recovery to a Tof Ratio of 0.9 we will need a total of 50 patients to assess neuromuscular recovery on both ipsi- and contralateral extremities with the Tof Cuff.

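### The rule for acceptable cuff–EMG agreement carries no confidence bound, so a cuff lying on the sponsor's own limit passes about half the time, and one slightly outside passes too often in a group of 50

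*Combined protocol and SAP*

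**What the plan says.** Section 7 (Statistics) describes the main comparison as follows: "Recovery of neuromuscular block will be compared by the Bland–Altman analysis for repeated measurements for TOF cuff vs. EMG". It explains the limits by saying "The limits of agreement capture 95% of differences between the compared devices", and then gives the criterion: "We defined clinically acceptable agreement as a bias <0.025 and limits of agreement within -0.050 to 0.050". The criterion has no confidence interval, test, alpha or sidedness, and no other section supplies one. The ipsi-/contralateral comparison has a separate criterion of the same form: "A relative bias of <5% is defined acceptable".

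The abstract (Methods) and Section 3 both label the design: "This is an observational, non-inferiority trial in which we will compare the TOF cuff device to electromyography (EMG". Section 7.1 justifies the 200 patients of the agreement study only as a number "to ensure that reliable estimates of repeatability coefficient (r), bias (D), and limits of agreement (L) are obtained". The amendment then brings the total to 250. The alpha of 0.05 and the stated beta of 0.9 in Section 7.1 belong to a different calculation, on time to a TOF ratio of 0.9.

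**The concern.** The limits of agreement describe the spread of differences between devices. They are not confidence limits, and they are themselves estimated with error. A non-inferiority claim needs the data to exclude the margin. An estimate that falls inside the margin does not do that. As written, the rule is applied to the estimated bias D and the estimated limits L, so nothing controls how often a cuff at or just beyond the sponsor's limits is called acceptable.

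That is the error a device validation most needs to guard against. Section 7.1 calls a TOF ratio of 0.9 clinically important for safe extubation. It also says that D and L are not known at that level or at deeper block.

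**Working it through.** **The plan's own figure.** No calculation supports the agreement rule. The only computed sample size concerns recovery time. With SD 18 and difference 42 − 30 = 12 min, n = (18 × (1.960 + 1.282)/12)² = 23.64, so 24 (two-sided, power 0.90). Allowing for half without complete recovery gives 24/0.5 = 48, against the stated 50. The figure reproduces, but it says nothing about D or L.

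**Inputs.** The margins are 0.025 and ±0.050 (Section 7); the bias criterion is unsigned and is read here as |bias|. Assumed: normal differences, m = 20 pairs per patient, between-patient share of variance 0.5–0.8.

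**Model.** Let σ be the total SD of the differences, with between- and within-patient variances σ_b² and σ_w². Write V = σ_b² + σ_w²/m for the variance of a patient's mean difference.
- Limits: D ± 1.96 s, where s² estimates σ_b² + σ_w².
- Var(D) = V/n.
- Var(s²) ≈ [2V² + (1 − 1/m)² × 2σ_w⁴/(m − 1)]/n.
- SE(limit)² = V/n + 1.96² × Var(s²)/(4σ²).

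**On the boundary, one limit binding.** With bias 0.02 and upper limit 0.050, σ = (0.050 − 0.020)/1.96 = 0.0153. The estimated limit is close to symmetric around its true value, which is the threshold itself. It falls below the threshold about half the time, and n cancels. Simulated acceptance is 50–53%.

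**On the boundary, both limits binding.** With zero bias and limits at ±0.050, both estimates must fall inside. If ρ is the correlation of the two outward errors, the probability is 1/4 + arcsin(ρ)/(2π). For independent differences, Var(D) is proportional to 1 and Var(1.96 s) to 1.96²/2 = 1.921. So ρ = 0.921/2.921 = 0.315 and the probability is 0.30. With the assumed clustering, simulation gives 26–31%.

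**Just outside.** With bias 0.02 and upper limit 0.0525, σ = 0.0325/1.96 = 0.0166. The excess is 0.0025.
- Share 0.5: V = 0.525σ². The second term of SE² is 0.552σ²/n. SE at n=50 is 0.0166 × √(1.077/50) = 0.00243, so z = 1.03 and about 15% pass. At n=200, z = 2.05 and about 2% pass.
- Share 0.8: V = 0.81σ². The second term is 1.264σ²/n. SE at n=50 is 0.0166 × √(2.074/50) = 0.00338, so z = 0.74 and about 23% pass. At n=200, z = 1.48 and about 7% pass.

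Simulation gives 16–24% at n=50 and 2–7% at n=200.

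**Under one-sided 95% bounds**

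| True state | Rule as written | With bounds |
|---|---|---|
| One limit at 0.050, n=50–200 | 50–53% | about 6–8% |
| Both limits at ±0.050 | 26–31% | about 1–2% |
| Upper limit 0.0525, bias 0.02, n=50 | 16–24% | about 3% or less |
| Upper limit 0.0525, bias 0.02, n=200 | 2–7% | about 3% or less |
| Limits ±0.040, bias 0, n=50 | 98–100% | 60–88% |
| Limits ±0.040, bias 0, n=200 | over 99% | over 99% |

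**The case against.** **This is a pilot estimation study.** The abstract and Section 7.1 do call it a pilot, no primary endpoint or alpha is attached to agreement, and the abstract ranks time to complete recovery as the most relevant outcome clinically. This lowers the severity. It does not remove the problem, because Section 7 still sets a pass/fail criterion.

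**The absence of intervals is inferred from silence.** This is fair. The plan never says that only point estimates count, and its Bland–Altman method is delegated to a cited paper that cannot be consulted here. But no interval is brought into the acceptance rule, and a rule should be readable from the plan.

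**The plan's own prior figures are not near the boundary.** At TOF ratio 0.7, Section 7.1 gives D −0.02 and L −0.035 to −0.012. Read as limits of agreement, these imply SD = 0.023/(2 × 1.96) = 0.0059. With one difference per patient at n=50, the 95% half-widths are about 0.0016 for the bias and 0.0028 for a limit, so both rules accept. At TOF 0.1, D is 0.05 and both rules reject. On these figures the verdict would not change. They do not cover the levels that Section 7.1 says are unknown.

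**Three stronger readings are tempting but unsupported.**
- A reader might infer that sample size never helps. That holds only exactly on the boundary. With a limit 10% too wide (0.055, bias 0.02), 3–9% pass at n=50 and under 1% at n=200.
- A reader might apply the rule to the roughly 25 complete recoveries expected among the 50 added patients. That number belongs to the recovery-time calculation. Section 6 plans paired readings throughout recovery, so patients who receive more relaxant still contribute pairs, and the purpose for which that cohort was added has its own 5% criterion.
- A reader might assume that a separate verdict in obese patients is required. The objectives name both BMI groups, but Section 7 does not demand a verdict in each.

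**Conclusion.** The criterion in Section 7 should be changed; this is a should-fix point. As written it accepts a cuff with one true limit on the boundary about 50–53% of the time, and with both limits on it about 26–31%, at any sample size. Slightly outside, the risk depends on n: for a limit of 0.0525 with bias 0.02 it is appreciable at n=50 (16–24%) and small at n=200 (2–7%). A verdict on about 200 patients is therefore reasonably protected against anything clearly outside the margins, while one on a subgroup of 50 is not. The obese group is 50 in the abstract and in Sections 3 and 4.1, whereas Section 7.1 gives 100 on a lower BMI cut-off.

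The boundary rates depend little on the assumptions where a single limit binds. The both-limits and outside-boundary rates depend on the assumed 20 pairs per patient and variance share of 0.5–0.8. None of this shows that the cuff is near the boundary, only that the rule could not tell.

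**What to change.** Keep the margins. Reword the criterion in Section 7 so that acceptable agreement is concluded only if the one-sided 95% upper confidence bound for |bias| is below 0.025 and the one-sided 95% outer bounds for both limits lie within −0.050 to 0.050. Compute the bounds from the patient-level variance components of the repeated-measures model, or by resampling patients, and name the method. Report D and L with these bounds. State in which groups a verdict will be drawn; elsewhere, report estimates and bounds without one.

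No new data are needed, but there are three costs. The claim is harder to reach in small groups: with true limits of ±0.040 and zero bias it passes about 60–88% at n=50 instead of 98–100%, though still over 99% at n=200. The approximate bounds give about 6–8% rather than 5% at the boundary for n=50–200. And because the interim analysis at 100 patients has been done, the change should be dated and declared as made after it.

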This is an observational, non-inferiority trial in which we will compare the TOF cuff device to electromyography (EMG). All patients will receive general total intravenous anesthesia (propofol/remifentanil/rocuronium). Patients will have the TOF cuff and EMG placed on the same extremity (hand for EMG, upper arm for TOF cuff). Measurements will be done during induction, maintenance and recovery from a moderate (GROUP 1) and deep (GROUP 2) neuromuscular block. Patients will enter the study in group 1 or 2 based on the required procedure. In other words, the procedure dictates the desired level of neuromuscular block (moderate or deep), not the study. We will perform a pilot study with 200 patients (150 patients with normal BMI ($< 30 \text{ kg/m}^2$) and 50 patients with morbid obesity ($> 35 \text{ kg/m}^2$) to ensure that reliable estimates of repeatability coefficient, bias, and limits of agreement are obtained. After 100 patients (50 non-obese/50 obese) we will perform an interim analysis and calculate the remaining number of patients needed to complete the study. The protocol was amended (19-11-2018) to include 50 extra patients to investigate relative bias between ipsi- and contralateral comparisons between TOF Cuff and EMG in patients. Total number of included patients will be 250. The interim analysis at 100 included patients showed a significant difference between the TOF Cuff and the EMG regarding the time to complete spontaneous recovery of neuromuscular block. The time to complete recovery is clinically the most relevant outcome as this reflects zero chance of residual NMB by definition. To increase the emphasis on time until full spontaneous recovery, the protocol was amended (19-6-19) to include 50 patients at the LUMC that were originally scheduled for inclusion at the Nederlandse Obesitas Kliniek (NOK). The very reason for this, is the fact that at the NOK, sugammadex reversal is routinely applied to facilitate quick changeover of patients. However, this practice interferes with the objective of

evaluating time until complete spontaneous (unreversed) recovery of the NMB. Transferal of 50 intended study subjects from the NOK to the LUMC will allow us to gather more data on the relevant final stages of the spontaneous recovery of NMB

1. Introduction

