Measurements will be done during induction, maintenance and recovery from a moderate (GROUP 1) and deep (GROUP 2) neuromuscular block. Patients will enter the study in group 1 or 2 based on the required procedure. In other words, the procedure dictates the desired level of neuromuscular block (moderate or deep) not the study. Patients will therefore enter the study in a non-randomized fashion.

In group 1, the target level of neuromuscular block is TOF 1-3 twitches (moderate neuromuscular block). Time to 90% depression of the first twitch will be recorded. Measurements will be performed during spontaneous recovery from T1 until full recovery to a TOF ratio of 1.0. After that, if time allows, a new rocuronium bolus will be given to reach a target TOF 1-3 twitches. Every 60 seconds, EMG measurements will be followed by TOF cuff.

In group 2 target depth of neuromuscular block after induction is 1 PTC (deep neuromuscular block). Time to 90% depression of the first twitch will be recorded. After that, spontaneous recovery will be allowed to a PTC of 10. After that, if time allows, a new bolus of rocuronium will be administered to again reach a PTC of 1 followed by spontaneous recovery. Again, EMG measurements will be followed by TOF cuff measurements on the other arm measurements at 5 min intervals.

[figure not shown]

Fig 1. Study outline

4. Study Population

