5.1.1 Anesthesia

Standard anesthesia monitoring will be applied (blood pressure, electrocardiography, plethysmography) and will include bispectral index (BIS module, Philips, Eindhoven, The Netherlands) to assess the level of hypnosis. Intravenous access will be obtained in the antecubital fossa on the EMG arm such that it doesn't hinder EMG measurements. Central body temperature will be measured at the nasopharynx and maintained at 35.5-37.5 degrees Celsius. Peripheral (skin) temperature measured on the palms of the hands on which neuromuscular monitoring is applied will be maintained at >32 degrees Celsius. All patients will be covered by forced warm air blankets. For induction and maintenance of anesthesia, propofol combined with remifentanil and rocuronium will be used. Depth of anesthesia is aimed at a bispectral index of 50 +/- 5.

In case of a moderate neuromuscular block (GROUP 1), rocuronium 0.6 mg/kg ideal body weight (IBW) bolus will be given at induction. After that, spontaneous recovery is allowed to a TOF ratio of 1.0. After that, if time allows, a new bolus rocuronium is given to reach the target depth of NMB of TOF 1-3. No reversal agent will be given in this group unless deemed necessary by the attending anesthesiologist.

In case of a deep neuromuscular block (GROUP 2), rocuronium 1.0 mg/kg IBW will be given at induction, aimed at a PTC of 1-2. If necessary extra rocuronium is given to reach the target depth of NMB. When PTC is 1 or 2, spontaneous recovery is allowed to a PTC of 10. After that, if time allows, a new bolus rocuronium is given to reach a target depth of NMB of PTC 1-2. For reversal, 4 mg/kg IBW sugammadex will be given at a NMB depth of 1-2 PTC.

Extubation in both groups will be performed if EMG TOF ratio values are > 0.9

The attending anesthesiologist will be responsible for the anesthesia and safety of the patient at any time during the experiment. He or she may decide to discard the protocol if this is required for safety reasons. Measurements will be performed and recorded in the CRF by a separate researcher in the operating theater.

In case of suboptimal surgical conditions, extra muscle relaxants may be given at any time as needed.

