Regarding precision, a one-way analysis of variance will be performed on the sets of consecutive TOF ratios measured by the same device during steady-state NMB maintenance conditions. The 95% repeatability coefficient (r) is defined as 1.96 times the standard deviation of the differences between 2 consecutive measurements.

Additionally we will construct Receiver Operating Curves (ROC) to assess the specificity and sensitivity of the TOF cuff versus EMG (gold standard) at various levels of NMB depth.

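### Repeatability is to be estimated from steady-state TOF ratios that the visible schedule does not supply, and the fixed EMG-then-cuff order in Group 1 adds an uncorrected, same-sign offset to the recovery bias

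*Combined protocol and SAP*

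**What the plan says.** **Objective.** Section 2 asks for the bias, limits of agreement and "precision of the TOF cuff relative to EMG during recovery of moderate and deep neuromuscular block".

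**Precision analysis.** Section 7 applies a one-way ANOVA to "sets of consecutive TOF ratios measured by the same device during steady-state NMB maintenance conditions". It then states: "The 95% repeatability coefficient (r) is defined as 1.96 times the standard deviation of the differences between 2 consecutive measurements". The same section says that the agreement analysis takes each device's repeatability into account. It sets acceptability at a bias below 0.025 and limits of agreement within ±0.050.

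**Schedule.** The abstract and section 3 say: "Measurements will be done during induction, maintenance and recovery from a moderate (GROUP 1) and deep (GROUP 2) neuromuscular block". The operative text is narrower.
- In Group 1, "the target level of neuromuscular block is TOF 1-3 twitches (moderate neuromuscular block"). After the bolus, section 5.1.1 continues: "After that, spontaneous recovery is allowed to a TOF ratio of 1.0".
- In Group 2: "When PTC is 1 or 2, spontaneous recovery is allowed to a PTC of 10".
- Section 6 lists onset and recovery data only.
- Section 5.1.2 (Calibration) adds three consecutive readings per device before rocuronium, with recalibration if they differ by more than 5%.

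**Order and interval.** For Group 1, section 3 says: "Every 60 seconds, EMG measurements will be followed by TOF cuff". Section 6 gives 30 s for the same comparisons. The text gives no EMG-to-cuff gap, no alternation of order and no time matching.

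**The concern.** The planned repeatability analysis needs several readings at an unchanging block. The visible schedule describes a bolus, then free or reversed recovery, with no period held at a stable TOF ratio. At one to three twitches the fourth response is absent, so the ratio is zero or undefined. A post-tetanic count has no ratio at all.

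At steady state the ANOVA and the stated definition of r give the same answer. On a rising ratio they do not: the ANOVA treats the rise as device error, and the SD of differences is inflated wherever the slope varies. The analyst would have to choose data and formula after seeing the readings. Precision is a stated objective, and section 7.1 makes a reliable estimate of r one purpose of the pilot.

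The reading order raises a related problem. If the cuff is always read after EMG while the ratio climbs, cuff minus EMG contains the recovery that took place between the two readings. That shift is always positive and enters the bias directly.

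**Working it through.** The plan gives no expected value of r and no gap, so there is no figure of its own to reproduce for this point. The sizes below are conditional on stated assumptions.

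**Inputs from the documents.** Time to TOF ratio 0.9 is 30 min (SD 18.0), and 47 min for EMG (section 7.1). The bias limit is 0.025 (section 7). Readings are every 60 s (section 3) or 30 s (section 6).

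**Assumptions.** Device SD is 0.01 or 0.02, with independent errors. The ratio rises logistically from 0.05 at time zero to 0.9, over a mean of 30 or 47 min. Between-patient CV is 18.0/30 = 60%. Section 7.1 does not give the time origin of its 30 and 47 min. If part of that time passes before the fourth twitch returns, the true slopes are steeper and the effects larger.

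**1. Repeatability from recovery readings.** For a pair of consecutive readings with true step b and device SD σ:
- ANOVA: r = 1.96 × √(2σ² + mean of b²)
- SD of differences: r = 1.96 × √(2σ² + variance of b)
- True value: r = 1.96 × √2 × σ, which is 0.028 for σ = 0.01 and 0.055 for σ = 0.02

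Hand check with a constant slope, σ = 0.01 and 60 s spacing: at b = 0.030, ANOVA r = 1.96 × √(0.0002 + 0.0009) = 0.065. At b = 0.0191 it is 1.96 × √(0.0002 + 0.000365) = 0.047. With a constant slope the SD of differences stays at 0.028; it inflates only when slopes vary.

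Simulation with varying slopes (4,000 patients per cell, non-overlapping pairs; each range covers mean 47 to 30 min):

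| Device SD, spacing | True r | ANOVA r | SD-of-differences r |
|---|---|---|---|
| 0.01, 60 s | 0.028 | 0.052–0.074 (1.9–2.7×) | 0.038–0.049 (1.4–1.8×) |
| 0.01, 30 s | 0.028 | 0.036–0.044 (1.3–1.6×) | 0.031–0.034 (1.1–1.2×) |
| 0.02, 60 s | 0.055 | 0.071–0.088 (1.3–1.6×) | 0.061–0.069 (1.1–1.2×) |
| 0.02, 30 s | 0.055 | 0.060–0.066 (1.1–1.2×) | 0.057–0.059 (1.03–1.07×) |

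**2. A drift-removing estimator.** A second difference (third reading, minus twice the second, plus the first) has error variance 6σ², and a locally straight rise cancels. So σ is estimated by the SD of second differences divided by √6. In the same simulation this gives r = 0.028 at σ = 0.01 (both spacings) and 0.055–0.056 at σ = 0.02 and 60 s. One straight line per patient does much worse (0.105–0.111 at σ = 0.01), because curvature is counted as error.

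**3. Order offset.** Offset = slope × gap. Average slopes are 0.9/47 = 0.0191 and 0.9/30 = 0.0300 per minute.

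| Assumed gap | Offset | Share of 0.025 |
|---|---|---|
| 5 s | 0.0016–0.0025 | 6–10% |
| 10 s | 0.0032–0.0050 | 13–20% |
| 30 s | 0.0096–0.0150 | 38–60% |

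At these slopes the offset alone equals 0.025 at a gap of 0.025/0.0300 = 0.83 min (50 s) to 0.025/0.0191 = 1.31 min (78 s). On the logistic curve a 30 s gap averages 0.009–0.014, with a local peak of 0.021 at a 30 min rise. A patient recovering in 12 min (30 − 18) would peak at about 0.054.

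**4. Interpolation.** Take EMG at the cuff time as (1 − w) × earlier reading + w × later reading, with w = gap/interval. Its error variance is [1 − 2w(1 − w)] × EMG error variance, so 2w(1 − w) × that variance must be added back for the limits of agreement. Check at a mean of 30 min, 60 s readings and both SDs 0.01 (true SD of differences √2 × 0.01 = 0.0141):
- 10 s gap: raw bias 0.0047 falls below 0.0001; SD 0.0131, or 0.0141 after add-back.
- 30 s gap: raw bias 0.0141 falls below 0.0001; SD 0.0123, or 0.0141 after add-back.

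Without the add-back, the half-width of the limits would narrow from 0.0277 to 0.0257 (10 s) or 0.0240 (30 s).

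**The case against.** **Maintenance is named, and the study outline figure is missing from the text reviewed.** This stands. A reader might infer that no steady-state readings exist. The documents do not support that: the visible text attaches no readings to maintenance, but the figure might.

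**The post-calibration triplets are scheduled and free of drift.** True, but they precede rocuronium. They are also screened by the 5% rule, so accepted sets are selected for closeness. They cannot stand in for precision under block.

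**No acceptance limit is set for r, and the harm arises only if recovery readings are substituted.** Both are correct, and they limit severity. How r enters the agreement analysis lies in a cited source that was not available. Precision is still a stated objective, and the text schedules no other TOF ratios under block.

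**The largest inflation belongs to the worst cell.** This stands. At SD 0.02 and 30 s the excess is only about 3–18%, so the whole range must be quoted.

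**The offset is minor.** At a 5 s gap it is. Two stronger inferences are tempting. The first is that reading order explains 30 versus 47 min. It does not: 17 min at these slopes is 17 × 0.0191 = 0.33 to 17 × 0.0300 = 0.51 ratio units, far above any offset computed here. The second is that the offset by itself breaches the bias limit. The gap is not documented, so this cannot be claimed, although steeper local slopes prevent ruling it out. Nor should the offset be asserted outright for Group 2 ratios after reversal. The explicit EMG-then-cuff order there concerns the 5-minute readings, and section 6 carries it over only by back-reference.

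**Second differences are not foolproof.** This stands; the limits are given with the fix.

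**Conclusion.** The point holds, as something to correct rather than a fatal flaw. The visible text does not schedule the steady-state TOF ratios on which section 7 rests r, and it does not say what replaces them. If recovery readings are used, r is overstated by about 1.1 to 2.7 times with the ANOVA and 1.03 to 1.8 times with the SD of differences. This assumes a device SD of 0.01–0.02, 30–60 s spacing and a rise from 0.05 to 0.9 over a mean of 30–47 min. A faster rise makes it worse.

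The Group 1 reading order adds a positive offset to cuff minus EMG, from about 0.002 (5 s gap) to 0.010–0.015 (30 s gap) at average slopes. That ranges from negligible to more than half of the 0.025 limit, and it is avoidable at analysis. Confidence is medium, because the gap, the device SD and the time origin of the recovery times are not in the documents, and because it could not be checked whether the cited Bland–Altman method handles lag.

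**What to change.** **In section 7, state which readings supply r.** If documented sets at a stable TOF ratio exist, keep the present definition. If not, do not apply the one-way ANOVA to raw recovery readings. Use r = 1.96 × √2 × (SD of second differences/√6), per device:
- on equally spaced recovery TOF ratios with the fourth twitch present and no bolus or reversal inside the triple, at the shorter interval available;
- labelled as short-interval repeatability during recovery, covering TOF ratios and not post-tetanic counts;
- with readings after reversal reported separately, and the number of contributing patients shown for each BMI group.

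**For bias,** interpolate EMG to the cuff time where reading times exist, and add back 2w(1 − w) × EMG error variance for the limits of agreement. Where times are missing, show the bias over a stated range of gaps.

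**Reconcile** the 60 s interval in section 3 with the 30 s interval in section 6.

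**Cost and limits.** The change needs SAP wording and modest code, with no extra patients and no change to measurements. Section 6 lists milestone times but not a time per reading, so for patients already measured only the gap-range display may be possible. The estimator assumes roughly independent errors; at serial correlation 0.3 it gives 0.022 against 0.023 by the plan's own definition, a small loss. It reads about 20% high (0.034 against 0.028) if the rise averages 15 min at 60 s spacing. At 30 s spacing it reads 0.036 for a 5 min recovery and 0.066 for 3 min, which is why readings after reversal are kept apart. High-BMI data may be sparse, since section 11.1 places those patients at the clinic where the abstract says reversal is routine. The transfer of 50 patients may ease this, but the text does not give their BMI group.
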